To increase follow-up response rates and with the approval of OFA, alternative follow-up data collection procedures were developed by the RIDGE and evaluation teams for one service site that enrolls most of the impact study participants at about 78%, Franklin CBCF. Many impact study participants from the Franklin CBCF service site go on to participate in a Department of Labor initiative immediately following their release from prison. As part of this initiative, participants are bussed from the Franklin CBCF to an American Jobs Center. TYRO Couples RCT participants who are part of this initiative are invited to complete a paper follow-up survey on the Thursday prior to the bus taking participants to the American Jobs Center the following Monday morning. Eligible participants who completed the survey will be handed a physical \$50 gift card upon boarding the bus. This follows guidelines of prisons where no monetary incentives can be administered on the premises. To be eligible for the follow-up survey, participants must have a signed consent form on file and have taken either the nFORM entrance survey or the local evaluation baseline survey. Evaluation staff will coordinate with program staff to ensure only those who are eligible for the follow-up survey are offered it. Paper surveys will be sealed in an envelope where they are given to a team member certified in protecting human research participants to enter the surveys into Qualtrics. Paper surveys are to be kept in locked storage at RIDGE offices and will be stored for a minimum of three years before being destroyed in accordance with IRB guidelines. This process is set to begin in May 2024.

Table 5. Key features of the data collection

Study group	Data source	Timing of data collection	Mode of data collection	Party responsible for data collection	Start and end date of data collection
Intervention (on-demand)	Survey Wave 1 (nFORM baseline and local evaluation baseline surveys)	Immediately following informed consent and randomization during orientation (within 1-2 weeks of enrollment)	In-person paper survey	RIDGE Staff	April 11, 2023 – November 30, 2024
	Survey Wave 2 (nFORM exit and local evaluation post-surveys)	Six weeks after program enrollment	In-person paper survey	RIDGE Staff	May 23, 2023 (or February 2023 for pilot cohort) – January 11, 2025
	Survey Wave 3 (Local evaluation follow-up survey)	Six months after program enrollment; Between three to six months after program enrollment at Franklin CBCF	Online via a QR code or email link; over the phone; in person paper survey if in the eligible Franklin CBCF group	MER Staff or RIDGE facilitator if in the eligible Franklin CBCF group	October 2023 – May 31, 2025 for all locations aside from Franklin CBCF; For Franklin CBCF- May 2024- May 31, 2025

Study group	Data source	Timing of data collection	Mode of data collection	Party responsible for data collection	Start and end date of data collection
Counterfactual (in-person)	Survey Wave 1 (nFORM baseline and local evaluation baseline surveys)	Immediately following informed consent and randomization during orientation	In-person paper survey	RIDGE Staff	April 11, 2023 (or January 2023 for pilot cohort) - November 30, 2024
	Survey Wave 2 (nFORM exit and local evaluation post-surveys)	Six weeks after program enrollment, immediately following the last primary workshop session	In-person paper survey	RIDGE Staff	May 23, 2023 (or February 2023 for pilot cohort) – January 11, 2025
	Survey Wave 3 (Local evaluation follow-up survey)	Six months after program enrollment; Between three to six months after program enrollment at Franklin CBCF	Online via a QR code or email link; over the phone; in person paper survey if in the eligible Franklin CBCF group	MER Staff or RIDGE facilitator if in the eligible Franklin CBCF group	October 2023 – May 31, 2025; For Franklin CBCF- May 2024- May 31, 2025

3. CONSORT diagram

The CONSORT diagram for this impact study (where random assignment occurs after consent) can be found in the appendix to this plan. The data used to complete the CONSORT diagram were pulled on July 22, 2024.

D. Analysis

This section describes the plans for defining the analytic sample, assessing baseline equivalence, cleaning data, handling missing data, and addressing potential crossover and contamination. It also describes the analytic models for estimating program impacts and planned sensitivity analyses.

1. Data preparation

Raw data sets will be cleaned and prepared for analysis using the R Studio statistical software. nFORM survey responses and participant information (e.g., study group assignment) will be downloaded using the Data Export feature of nFORM, and local evaluation survey responses will be exported from Qualtrics as Excel files. All exports will be imported into R and cleaned separately before data sets are merged into a final, wide format file for analyses using nFORM Client ID as the unique identifier for matching observations. Planned procedures for data cleaning and handling missing data are detailed below.

Inconsistent or seemingly inaccurate data

To address participant feedback about the relevance of some local evaluation survey items, evaluators added skip logic to local evaluation surveys in October 2023 for relationship attitudes and behaviors (which are used in a secondary research question because they are not applicable to the entire sample).

Measures for primary research questions only use items that are applicable to the entire study population. However, secondary exploratory research questions include items that are not applicable to the entire study population as not all study participants report being in a committed relationship.

See Figure A.4. for a full breakdown of survey items, including which had skip logic added.

In addition, preliminary analyses showed relationship questions had 25-28% of missing responses. After the skip logic was added, participants who reported not being in a committed relationship were permitted to skip questions about relationship behaviors, and participants who reported not being currently employed were permitted to skip some questions about employment behaviors. Some participants may have responded to these questions at baseline but not been shown the same questions at follow-up due to the added skip logic. For example, a participant might have been in a relationship at the time of the baseline survey completion, but not at the time of the follow-up survey completion.

Because technology restrictions in prison facilities require the administration of paper surveys, it is possible for respondents to answer questions in violation of skip/display logic if they misunderstand the instructions on the paper survey. To err on the side of retaining as much of the sample as possible, we will not deem a response invalid if the participant response to a skip logic question incorrectly (answering "no" instead of "yes") but then proceeds to answer the follow-up question accurately.

Participants who report inconsistencies in the number or age of their child(ren) between nFORM and local evaluation surveys at the same time point will have their answers be assigned as the response they gave on the nFORM ACS or entrance survey.

Outlier values, defined as extremely low or extremely high values that are likely introduced to the dataset due to an input error, for variables such as participant's age, children's age, and income, which participants manually input, will be recoded to the 99th percentile for the sample if necessary. We will top-code any values above the 99th percentile with the average of all values below this threshold.

Duplicate data

In the case of duplicate data, where one participant has taken the same local evaluation survey more than one time, we plan to take the following approach:

- Check for incorrectly entered Client IDs that inaccurately flag surveys as duplicates. Using the name and/or DOB fields on the local evaluation survey, we will check that responses that appear to be duplicates were in fact collected from the same participant multiple times (i.e., are true duplicates). Common instances of this occurring could be if a participant did not finish a survey and re-took it later on, or if they took the follow-up survey twice for the incentive. If the survey is not a true duplicate, we will correct Client IDs as necessary.
- For surveys identified as true duplicates, we will check for completeness. If one duplicate survey is complete while the other is not, we will use the most complete survey to minimize item non-response.
- If both duplicate surveys are equally complete, we will use the first response that a participant submitted, as indicated by the Recorded Date field on the Qualtrics data export. This approach is

only applicable to the follow-up survey. Because program staff enter paper survey data into Qualtrics, there should not be duplicate baseline and post-surveys.

Missing data

Survey nonresponse

Because outcome measures for this impact study are constructed from survey items from both nFORM and the local evaluation surveys, survey nonresponse on either the nFORM baseline survey, local evaluation baseline survey, nFORM exit survey, local evaluation post survey, or local evaluation follow-up survey can lead to sample attrition. Survey response rates are monitored on an ongoing basis through bi-weekly CQI reports produced by the evaluation team using the nFORM Survey Completion Summary operational report and Qualtrics response data export feature. Response rates are calculated by dividing the number of participants who responded to each survey by the number of participants who were eligible to respond to that survey up to that time point. If CQI reports show that survey response rates are below intended targets, the CQI team brainstorms and implements strategies to increase response rates to minimize sample attrition caused by survey nonresponse. Reasons for survey nonresponse, to the degree that they are known, will be reported in the CONSORT diagram. Individuals with survey nonresponse at the follow-up time point will not be included in the analytic sample; the analysis for each outcome will use complete case data.

Item nonresponse

Item nonresponse can also lead to sample attrition for particular outcome measures if participants skip survey items that are aligned with the research questions for this study. Item nonresponse is calculated by dividing the number of participants who respond to a survey item by the number who were eligible and able to answer a question based on skip/display logic. As stated in the data preparation section above, respondents taking paper surveys may violate skip/display logic, and invalid responses will be dropped before item-level response rates are calculated. We will also note what proportion of the sample skipped out of the relationship and employment attitude questions to give context to the item nonresponse.

Constructed outcome measures

Each of the outcomes for the primary research questions for this study are constructed averages using multiple, related survey items. Sufficiently high item nonresponse among items used to construct outcome measures will lead to sample attrition for that outcome. The evaluation team plans to use an 80% threshold as the cutoff for constructed measures; respondents who answer less than 80% of survey items associated with a constructed measure will be dropped from the analysis for that outcome. The constructed average for each participant who has answered at least 80% of associated survey items will be calculated by dividing the sum of their survey answers by the number of items they answered. For example, if a participant answers 8 out of 10 survey items associated with a construct, their average for that outcome measure will be the sum of their 8 answers divided by 8. The evaluation team does not plan to use imputation for multi-item constructed outcomes with 20 percent or fewer missing items. A sensitivity analysis will be conducted to see if and how results would change with a 70% threshold cutoff instead of an 80% cutoff.

2. Attrition and analytic sample

The analytic sample for each outcome construct identified in Table 2 will consist of study participants who have a non-missing value at baseline and follow-up time points for that construct (complete case). The size of the analytic sample may vary by outcome measure based on the prevalence of item non-response missing data at the baseline and follow-up surveys for the items used to create those composite measures. For attitudinal outcomes related to economic stability, and finances, all respondents with complete case data will be included in the analytic sample. For relationship behavior outcomes, participants will be included in the analytic sample if they report being in a committed relationship at the time the survey was administered (i.e., do not choose 'no' for the skip logic question 'Are you currently in a committed romantic relationship?'). Because this skip logic was added to the local evaluation surveys belatedly (in October 2023), this condition will only apply to those respondents who took a survey with this skip logic. For those respondents who took a survey before this relationship skip logic was added, all participants who have complete case data will be included in the analytic sample in response to the secondary research question.

All outcome measures for this study are constructed averages calculated using a number of theoretically and empirically related survey items. As mentioned in the previous section, a respondent who answers some but not all survey items in a given outcome construct will have their outcome value assigned as missing if they do not respond to at least 80% of the items in the construct. We will not impute missing baseline or outcome data for our analyses. Based on the recommendation from ACF, we will use the cautious attrition threshold from the What Works Clearinghouse (WWC) to assess whether attrition can be considered high or low.

Assessment of baseline equivalence

Per the WWC's standards, we will use effect sizes (i.e., standardized mean differences), to examine the baseline equivalence between the study groups. Effect size is defined as the difference between the intervention group mean and the comparison group mean, divided by the pooled standard deviation. We will calculate the effect size for demographic characteristics (such as gender, age, and race/ethnicity, as reported on the nFORM Applicant Characteristics Survey) and each baseline outcome of interest depending on the type of variable: Hedge's g , for continuous variables; and Cox's index, for dichotomous variables. We can determine baseline equivalence by comparing each outcome's effect size using the WWC standard, which suggests that if the corresponding effect size is 0.05 or less in absolute value, it is considered "small," and we can conclude that it satisfies baseline equivalence without statistical adjustment. However, if the effect size falls between 0.05 and 0.25, it is considered "moderate," and it will require a statistical adjustment to meet baseline equivalence (we will use statistical adjustments such as regression adjustments or matching/weighting). Lastly, in the case that the effect size is greater than 0.25, it will be considered "large", which shows that the differences at baseline are too large to meet WWC standards, even with statistical adjustments. In that case, we will apply appropriate caveats to any interpretation of the results.

Condition crossover

At the primary RCT enrollment site, Franklin CBCF, condition crossover is not possible due to restrictions put in place when designing the implementation of the two delivery formats. If a participant who was

assigned to the on-demand group attempts to attend the in-person classes, the facilitators will not allow them to sit in on in-person classes and will remind them that they are to complete the curriculum via tablet in the designated classroom. Tablets must be checked out to be used in the designated space, and a program staff member will be present to verify that participants who attempt to check out a tablet have been assigned to the on-demand group.

Other facilities participating in the RCT may not have the same restrictions in place to prevent condition crossover. In all participating facilities, facilitators have been trained on the design of the study and understand the importance of enforcing adherence to the condition to which a participant has been assigned. The evaluation team has a record of which study group each participant should have been assigned to based on the last digit of the inmate number and the randomization schema for each cohort, so cross-over to a different treatment condition can be flagged, and the prevalence of condition crossover will be disclosed in the final report.

3. Analytic approach

Modeling approach

Due to the nature of the continuous dependent variables of interest, we plan to fit a model using linear regression for all primary and secondary analyses for this study. We will model curvatures to ensure that the model is still linear in the parameters by doing re-expressions of the independent variables to fit a curve. We will also check the adequacy of the model to meet the remaining assumptions of a linear model (normality, multicollinearity, homoscedasticity, and independence) by reviewing the diagnostic plots and transforming our variables accordingly, if necessary. However, based on the nature of the survey data we will be using, we do not anticipate needing to fit a nonlinear model.

Analyses will be conducted using the R Studio statistical software package. The basic model for this impact evaluation will include a dummy variable for intervention group assignment, equal to 1 if a participant was randomly assigned to receive the curriculum on-demand via tablet, and a participant's score at baseline as the main predictors of each outcome measure at follow-up. To enhance the precision of the impact estimates, we plan to include several other covariates in our models. For all outcome analyses, we will control for participant age, gender, and race, as well as the timing of a participant's follow-up survey (number of days between program enrollment and follow-up survey completion). We will also consider including a facility indicator to denote which site the participant received services at. Additionally, we will include any demographic variables that were shown to be significantly different between study groups during baseline equivalency analysis. For the healthy relationship attitudes outcome, we also plan to include relationship status at baseline as a covariate. This will only be available if a participant reports being in a relationship at baseline and at follow-up.

Table 6. Covariates included in impact analyses

Covariate	Description of the covariate
Age	Age (in years) as of the baseline data collection, as reported on the ACS
Gender	Self-reported gender identification as of the baseline data collection, as reported on the ACS
Race	Self-reported racial identification as of the baseline data collection, as reported on the ACS

Covariate	Description of the covariate
Timing of follow-up survey	Number of days between program enrollment date and date of follow-up survey completion to control for variation in survey timing
Relationship status (relationship attitude and behavior outcomes only)	Relationship status (1 = in a committed relationship, 0 = not in a committed relationship) as of the baseline data collection, as reported on the ACS

4. Sensitivity analyses for primary research questions

We plan to conduct several sensitivity analyses to test the robustness of our results. First, and as mentioned earlier in the plan, we will conduct a sensitivity analysis to see if and how our outcome construct measures change if we use 70% as a threshold for non-missing items instead of 80% as a threshold.

[figure not shown]
Next, we will conduct an analysis to see how outcome construct measures change if we use mean imputation to replace missing items in the multi-item scales used to create our outcome variables. This is the mean based on observed values from the rest of the sample for that item. The current plan is not to use any imputation for outcome measures, including constructed outcomes from multiple survey items, and instead to make the denominator for the calculation of the average score be equal to the number of non-missing items in that construct.

Finally, we plan to conduct a sensitivity analysis regarding the timing of the follow-up survey. Given changes in follow-up data collection protocol at Franklin CBCF, we anticipate that some respondents will have taken their paper follow-up survey earlier than intended. The sensitivity analysis will repeat our analyses using only people who completed their follow-up survey within the intended data collection window (5-7 months post-enrollment).

5. Analyses addressing secondary research questions

The analytic approach for answering the secondary research question about partner relationship behaviors will be the same as the approach taken for the primary research questions.

Figure A.3. CONSORT diagram for individual clients, for studies in which consent occurred before assignment

Eligible for 6-month post-enrollment follow-up (n = 206)

To be eligible, a participant must have provided consent and taken either the nFORM baseline or local evaluation baseline survey

Completed follow-up (n = 64)

Data collection: July 1, 2023-July 22, 2024

Reasons for non-completes (n = 1) (that can be accounted for)

Consent revoked (n = ___), declined survey (n = ___), deceased (n = ___), dropped out (n = 7), moved (n = ___), incarcerated (n = 1)

Eligible for 6-month post-enrollment follow-up (n = 190)

To be eligible, a participant must have provided consent and taken either the nFORM baseline or local evaluation baseline survey

Completed follow-up (n = 52)

Data collection: July 1, 2023-July 22, 2024

Reasons for non-completes (n = 1) (that can be accounted for)

Consent revoked (n = ___), declined survey (n = ___), deceased (n = ___), dropped out (n = 4), moved (n = ___), incarcerated (n = 1)

Figure A.4. Survey items linked to research questions

Measure	Item Response	Are these items linked to a primary research question?	Are these items linked to a secondary research question?
Partner relationship beliefs 8 items			No
Partner relationship attitudes/expectations 8 items	Added skip logic allows participants to only respond to these items if they indicate that they are currently in a committed relationship.	No	Yes
Partner relationship behaviors 2 sets of questions: 7 items 11 items			Yes (only the first set of items containing 7 items)
Finance attitudes 7 items	Shown to all participants	Yes	No
Finance behaviors 4 items		No	No
Employment attitudes 8 items	Shown to all participants	Yes	No
Employment behaviors 5 items	Added skip logic allows participants to only respond to these items if they indicate that they are currently employed.	No	No
Parenting attitudes 8 items	Added skip logic allows participants to only respond to these items if they indicate that they have at least one child.		
Parenting behaviors Based on child's age 11 items (>age 6 & = < age 12), 9 items (< age 1 & = <6), 11 items (for child = <1)		No	No
Co-Parenting attitudes 5 items			

References

Bandura, A (1977). Self-efficacy: Toward a Unifying Theory of Behavioral Change. *Psychological Review*. 84 (2), 191–215.

Chou, S., & Liu, C. (2005). Learning effectiveness in a web-based virtual learning environment: A learner-control perspective. *Journal of Computer Assisted Learning*, 21(1), 65 - 76.

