1. For participants who report being in a relationship, what is the impact of the on-demand delivery (treatment) compared to the in-person delivery (counterfactual) of the TYRO Couples curriculum on **marriage/intimate partner relationship behaviors** six months after program enrollment?
2. For participants who report being in a relationship, what is the impact of the on-demand delivery

¹ Source: Chou, S., & Liu, C. (2005). Learning effectiveness in a web-based virtual learning environment: A learner-control perspective. *Journal of Computer Assisted Learning*, 21(1), 65 - 76.

(treatment) compared to the standard in-person delivery (counterfactual) of the TYRO Couples curriculum on **marriage/intimate partner relationship attitudes** after program completion?

3. Primary and secondary outcome measures

For this impact evaluation study, the intervention that will be tested is the delivery format of the TYRO Couples curriculum. The research questions are framed to determine if program participants who are randomly assigned to the TYRO Couples curriculum through an on-demand format will derive more benefits compared to those who are assigned to the TYRO Couples curriculum in a standard, in-person format.

Primary research questions are applicable to the entire population in the study and will be measured six months after the intervention has ended. This study focuses on employment and financial attitudes as the primary research questions. Finding and maintaining a job, which is one of the top priorities participants will have after release, has been noted in criminal justice research to reduce former prisoners' chances of reoffending (Visher, Debus, and Yahner, 2008). Subsequent secondary research questions focusing on relationships are only applicable to the study population who report being in a relationship. However, all research questions are relevant to the TYRO Couples Curriculum as well as consistent with the study's logic model.

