Outcome measures in this study were created for this evaluation and are not based on already-validated scales. Using the local evaluation baseline survey, we will generate a correlation matrix between items in a given construct to ensure that theoretically related items are also empirically related in our data set. Items that are not strongly correlated with other items in a construct will be removed as necessary. Factor analysis will be used to ensure that all construct items hang together (using an alpha of 0.60 or higher as the threshold). We will then create a composite measure by taking an average of the scores on each non-missing item in the construct. For composite measures, a change score will be calculated between a participant's pre-program composite score and six-month-post-enrollment follow-up composite score. If construct items do not meet the 0.60 threshold, that outcome will be removed. An alpha value of 0.60 is the minimally acceptable value that will be used for scale construction.

We will create a composite score by taking the average of multiple individual items. For these composite measures, our plan is to use 20% as a threshold for allowable missing items. This plan is contingent on the final distribution of missing data in our dataset. With a 20% threshold, if a respondent is missing more than 1 item used for creating the employment construct or more than 2 items for creating the financial construct, the respondent will be assigned a missing value for that construct. We will not impute truly missing values for outcomes. To create a construct score, the average will be divided by the number of non-missing values in the construct.

Table 1. Description of outcome measures used to answer impact analysis primary research questions

Research question #	Outcome name	Description of the outcome measure and its properties	Source of the measure	Timing of measure
1	Employment Attitudes	
The outcome measure is a scale (value range of 1=strongly disagree to 5=strongly agree) calculated as the average of eight survey items related to employment attitudes.
 
Sample item: I have the skills I need to get a decent job.
	Local evaluation follow-up-survey	Six months after program enrollment

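### A primary outcome with alpha below 0.60 is removed with no fallback, and its items and missing-item limit are left open, so a primary question may go unanswered or be rescored late

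*Combined protocol and SAP*

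**What the plan says.** Section A.3 (Primary and secondary outcome measures) names the two primary outcomes: "This study focuses on employment and financial attitudes as the primary research questions". On their pedigree it says: "Outcome measures in this study were created for this evaluation and are not based on already-validated scales". Table 1 gives eight employment items and seven financial items.

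The scales are to be settled on the trial's own data: "Using the local evaluation baseline survey, we will generate a correlation matrix between items in a given construct". Three rules follow in the same section.

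- **Items:** "Items that are not strongly correlated with other items in a construct will be removed as necessary". No correlation value is given.
- **Whole outcome:** an alpha of 0.60 is the minimum, and "If construct items do not meet the 0.60 threshold, that outcome will be removed". No substitute outcome, fallback score or reporting rule is named.
- **Missing items:** "our plan is to use 20% as a threshold for allowable missing items", followed by "This plan is contingent on the final distribution of missing data in our dataset". The section converts the 20% into counts: the score is set to missing beyond 1 missing employment item or 2 missing financial items.

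Section D.1 (Constructed outcome measures) and section D.2 (Attrition and analytic sample) restate the limit as at least 80% of items answered, with no contingency. Sections D.1 and D.4 plan a sensitivity analysis at 70%. Nothing in section D withdraws the contingency in A.3.

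**The concern.** The removal rule covers all constructs, so it covers the two primary ones. If either scale misses the cut, the plan as written leaves one of two primary questions without an answer and does not say what will be reported in its place. Because the scales are new, nothing in the documents shows that they will clear 0.60.

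The other two rules are open-ended. Item removal has no cutoff, so two analysts could build different scores from the same baseline data. The missing-item limit has no trigger, no alternative value, no date and no blinding. It depends on the final pattern of missing data, so it can be reset once follow-up data exist. That would change who is in the primary analysis and how they are scored. Some follow-up data were already in hand: Figure A.3 shows 64 + 52 = 116 completed follow-ups at the July 2024 data pull.

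**Working it through.** **1. The plan's own missing-item counts.** Inputs: 8 and 7 items (Table 1) and the 20% limit (A.3). The limit in items is 0.20 × k.

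| Scale | 0.20 × k | Rounded down | Rounded to nearest | Rounded up | Stated in A.3 |
|---|---|---|---|---|---|
| Employment, k = 8 | 1.6 | 1 | 2 | 2 | 1 |
| Financial, k = 7 | 1.4 | 1 | 1 | 2 | 2 |

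No single rounding rule gives the stated pair (1, 2). Employment follows from rounding down: 1/8 = 12.5% missing. Financial does not: 2/7 = 28.6% missing, or 71.4% answered. That fails the 80% rule of D.1 and D.2 and already meets the 70% sensitivity cutoff. Under a true 80% rule each scale allows 1 missing item (1/7 = 14.3%); under 70% each allows 2.

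**2. What the choice of count does.** Assume, for illustration only, that financial items are missing independently with probability p. The share losing the score is P(X > m), with X ~ Binomial(7, p) and m the number allowed missing.

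| p | m = 1 | m = 2 |
|---|---|---|
| 2% | 0.8% | 0.03% |
| 5% | 4.4% | 0.4% |
| 10% | 15.0% | 2.6% |

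**3. Chance that the gate removes an outcome.** The documents give no alphas, so true values are assumed. For n, 206 + 190 = 396 were eligible for follow-up in July 2024 (Figure A.3). This is an upper figure for local baseline surveys, since eligibility required either the nFORM or the local baseline survey. The target analytic sample of 768 (C.1) is the second case. Feldt's result is (1 − α)/(1 − α̂) ~ F(n − 1, (n − 1)(k − 1)), so P(α̂ < 0.60) = P(F < (1 − α)/0.40).

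| True alpha | n = 396, k = 8 | n = 396, k = 7 | n = 768, k = 8 | n = 768, k = 7 |
|---|---|---|---|---|
| 0.55 | 0.944 | 0.942 | 0.986 | 0.985 |
| 0.60 | 0.508 | 0.507 | 0.505 | 0.505 |
| 0.62 | 0.258 | 0.260 | 0.179 | 0.181 |
| 0.65 | 0.044 | 0.045 | 0.008 | 0.009 |
| 0.70 | <0.001 | <0.001 | ~0 | ~0 |

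A simulation with equally correlated normal items agreed to within about 0.02. At n = 396 and k = 8, the 95% interval around an observed alpha of 0.60 is 0.54 to 0.66. The calculation holds the item set fixed; dropping weak items first would tend to raise alpha.

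**4. What separates a scale just below the cut from one just above.** If random error is the only difference, the standardised effect scales with the square root of reliability: √(0.59/0.61) = 0.983, a change of under 2%. This says nothing about a scale far below the cut.

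**5. Item removal feeds back into the limit.** At 20%, rounded down, 5 to 9 items allow 1 missing and 4 items allow none. An unsettled item list therefore leaves the missing-item count unsettled too.

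**The case against.** **The gate is a fixed number, stated in advance.** On the natural reading it uses the baseline survey, which section C.2 places before any workshop hours. It then cannot respond to treatment effects. This stands. A reader might infer selective reporting, or that an outcome would be dropped after its results are known. The documents do not support that: they give no date for the check and do not say that a removed outcome would be concealed. They also do not show what was registered, so the point concerns the plan's stated primary outcomes only. One gap remains: A.3 names the baseline survey for the correlation matrix but does not name the survey wave for alpha.

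**The firm 80% rule and the 70% sensitivity analysis largely settle the limit.** This stands in part. They reduce the problem to a conflict between A.3 and D.1–D.2, but do not cancel the contingency, and the financial count in A.3 breaks both the 20% and the 80% wording.

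**The 51% figure is true of any cutoff placed at the true value.** This stands. It is not an estimate for this trial, and the risk fades quickly above 0.65.

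**Low alpha can mean that the items do not measure one thing, and reliability can matter for bias.** This stands in part. Random outcome error alone does not bias a raw-scale difference in an intact randomised sample. Here, however, follow-up was 64 of 206 and 52 of 190 at the interim pull, and the plan adjusts for baseline scores. A noisy baseline score corrects imbalance only partly. That supports a clear caveat on a low-alpha result, but it does not require removing a primary outcome without a substitute.

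**Conclusion.** The concern holds in limited form, as something that should be changed. As written, the plan can leave one of its two primary questions unanswered, and it leaves the item lists and the missing-item limit open to late choice. The size of the first risk is unknown because no alphas are reported. At n = 396 it runs from about 94% at a true alpha of 0.55, through 51% at 0.60 and 26% at 0.62, to 4% at 0.65 and near zero at 0.70. These figures assume Feldt's distribution and a fixed item set.

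The gate does not itself inflate type I error if it is run on pooled baseline data; the harm is the lost question. For the limit, the harm is a conflict between sections, a financial count that matches neither percentage, and permission to change the rule after follow-up data exist. A reader might go further and infer that the limit would be chosen to favour a result. The text ties it to the distribution of missing data, not to arm differences, so that is not supported.

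**What to change.** 1. **Replace the removal rule in A.3.** Suggested wording: *Both primary outcomes will be analysed and reported whatever their alpha. If alpha is below 0.60, the result will carry a low-reliability caveat, and any item-level results will be labelled descriptive.* The descriptive label avoids adding up to 15 (8 + 7) further tests without a multiplicity rule.
2. **Settle the missing-item limit.** Delete the contingency sentence. Keep at least 80% answered as the primary rule, with 70% as the sensitivity analysis. Correct the financial count in A.3 to no more than 1 of 7 items missing, and restate the counts if item selection changes the number of items.
3. **Close the item rule.** Give a numeric item-removal criterion and name the baseline survey as the source for alpha. Run item selection and alpha once, on pooled data without the arm variable, and freeze the item lists before follow-up data are analysed by arm. Wave 1 runs to November 30, 2024, so the SAP should say whether the run uses the baselines to date or waits for the full set; either works if it comes before the by-arm analysis.

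The cost is a few sentences and one run on baseline data. The downsides are that a primary result may carry a low-reliability caveat, and that somewhat more financial scores are set to missing than with 2 allowed: 4.4% against 0.4% at an assumed 5% item missingness.
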